4.4. Other Eligibility Criteria Considerations

Patient eligibility may require additional or repeat assessments such as safety labs, vital signs, or ECG during the Screening Period.

To assess any potential impact on patient eligibility with regard to safety, the investigator is referred to the Investigator Brochure for detailed information regarding warnings, precautions, contraindications, adverse events, and other significant data pertaining to the investigational product(s) used in this study.

4.5. Screening

Screening numbers will be assigned to each patient who signs an informed consent form and begins the Screening Period. Study site personnel will access the interactive voice/web recognition system (IWRS) to assign a screening identification number to a potential patient.

For patients who provide informed consent and subsequently do not meet eligibility criteria, or withdraw consent are considered screen failures and are not randomized. Study site personnel should ensure that the source record includes documentation for the screen failure (eg, medical history, eligibility criteria, procedures performed).

Patient numbers assigned to patients who become screen failures are not to be reused. Patient identification numbers will be assigned to eligible patients at randomization, as described in Section 4.6.

4.6. Method of Assigning Patients to Treatment Group and Patient Identification Number

After a patient is screened and the investigator determines that the patient is eligible for enrollment, the site staff will complete the Randomization Authorization Form and send it to the sponsor (Myovant Sciences GmbH) or sponsor designee per the instructions in the investigator site file. The sponsor (or designee) will approve the patient's enrollment in writing. Once the site has received approval, the patient may undergo the Baseline Day 1 visit. The site will randomize the patient to treatment by using the IWRS during the patient's Baseline Day 1 visit. The IWRS will assign the patient identification (ID) number. This number will identify the patient for the duration of the study. A study treatment kit number will be available at the site according to the randomization code.

4.7. Removal of Patients from Therapy

Patients may withdraw consent to participate in the study and discontinue treatment at any time for any reason. Investigators or the medical monitor may remove patients from therapy under this protocol for reasons of safety and/or lack of compliance as discussed below. Patients removed from therapy for any reason will undergo the assessments for the Week 49 visit on the Schedule of Activities. The End of Treatment is defined as the last dose of relugolix or 12 weeks after the last leuprolide acetate injection.

Follow-up visits to assess safety will be performed in all study patients. If the patient plans to start alternative androgen deprivation therapy less than 30 days after the End of Treatment visit, the Safety Follow-up visit may occur earlier, before the start of the alternative androgen deprivation therapy. Testosterone recovery will be evaluated in approximately 100 patients randomized to relugolix and approximately 50 patients to leuprolide acetate who complete 48 weeks of study drug treatment and, in the opinion of the investigator, are candidates for intermittent androgen deprivation therapy and will not be offered alternative androgen deprivation therapy upon completion of study therapy. These patients will return for the 60- and 90-day follow-up Testosterone Recovery visits.

The safety and/or compliance events shown in [Table 4-1](#) will result in the removal of patients from therapy either permanently or until the etiology of the problem has been identified and resolved.

Table 4-1 Removal of Patients from Treatment

Reason	Comment
Adverse event or intercurrent illness	Any intolerable adverse event to the patient that cannot be ameliorated by the use of adequate medical intervention, or that in the opinion of the investigator or medical monitor would lead to undue risk to the patient if dosing continued
Failed to meet eligibility criteria post randomization	If it is discovered after randomization that a patient failed to meet protocol entry criteria and continued participation poses an unacceptable risk to the patient's health
Dose hold	Relugolix dose hold that exceeds 10 consecutive days

Reason	Comment
Patient not meeting criteria for testosterone suppression to castrate level	Patients with disease progression while on study drug, assuming adequate testosterone suppression (testosterone level ≤ 50 ng/dL [1.7 nmol/L]), may receive radiotherapy as prescribed by the investigator. In the setting of rising PSA patients may also receive enzalutamide. For patients requiring other systemic antineoplastic therapy during the treatment period, the investigator should contact the medical monitor.
Laboratory abnormality defined by protocol: ALT or AST $> 8 \times$ ULN; or ALT or AST $> 5 \times$ ULN and persists for more than 2 weeks; or ALT or AST $> 3 \times$ ULN in conjunction with elevated total bilirubin $> 2 \times$ ULN or INR > 1.5 ; or ALT or AST $> 3 \times$ ULN with appearance of fatigue, nausea, vomiting, right upper quadrant pain or tenderness, fever, rash and/or eosinophilia ($> 5\%$)	If any of these liver test abnormalities develop, study drug should be discontinued immediately with appropriate clinical follow-up (including repeat laboratory tests, until a patient's laboratory profile has returned to normal/baseline status).
Confirmed QTc prolongation of more than 500 msec, in the absence of a pacemaker, as read by a cardiologist	If QTc prolongation of > 500 msec in the absence of a pacemaker occurs, the ECG must be repeated. Confirmed QTc prolongation, measured by Fridericia's formula [QTcF = QT/(RR $^{0.33}$)], will result in removal of the patient from treatment.
Patients who have a clinically significant decrease in visual acuity as evaluated by an ophthalmologist that may be related to study drug treatment	
Gross noncompliance with protocol	Patients who are, in the opinion of the investigator or the medical monitor, non-compliant with the protocol's requirements
Patient decision	Patients may permanently discontinue study treatment at any time for any reason. Following study drug discontinuation, patients should attend the protocol-required safety follow-up visit.
Sponsor discontinuation of study	The sponsor reserves the right to terminate the study anytime as described in Section 10.3.3. The sponsor will terminate this study following completion of study objectives, or earlier if deemed necessary.

Abbreviations: ALT, alanine aminotransferase; AST, aspartate aminotransferase; ECG, electrocardiogram; INR, international normalized ratio; QTc, QT interval corrected for heart rate; QTcF, QT interval corrected for heart rate using the Fridericia formula; ULN, upper limit of normal

Once study drug has been discontinued, all study procedures outlined for the Week 49 visit will be completed as specified in the Schedule of Activities (Section 1.1). The primary reason for study drug discontinuation will be recorded on the eCRF.

Patients who withdraw from treatment will not be replaced.

Should a patient fail to attend the clinic for a required study visit within the protocol-defined window, the site should attempt to contact the patient and reschedule the missed visit as soon as possible. The site should also counsel the patient on the importance of maintaining the assigned visit schedule and determine whether the patient can and/or should continue in the study based on previous non-compliance. Patients randomized to relugolix should be counseled to notify the investigator in the event of intercurrent illness to determine if the study drug treatment can be continued. Every effort should be made to ensure the patient's compliance with study drug treatment, including calling patients to reschedule missed visits.

In cases where the patient does not return for the rescheduled visit or cannot be reached to reschedule the missed visit, the site should make every effort to regain contact with the patient. The site should attempt at least 3 documented telephone calls and, if necessary, a certified letter to the patient's last known mailing address so that they can appropriately be withdrawn from the study with a primary reason of "Lost to Follow-up."

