Chronic stimulation by the GnRH agonist ultimately desensitizes the GnRH receptors, downregulating the secretion of gonadotropins, LH, and FSH, leading to hypogonadism and thus a dramatic reduction in testosterone and dihydrotestosterone, on which continued growth of prostate cancer cells depends. The fall in serum LH leads to a decrease in serum testosterone to castrate levels within 3 to 4 weeks after the start of treatment. Continued treatment maintains serum testosterone at castrate levels.

The decrease in testosterone production is generally reversible over time upon cessation of GnRH agonist therapy. However, testosterone production does not always return to baseline levels and may be related to the duration of GnRH agonist therapy, patient age, and other factors.

The flare phenomenon can be effectively prevented with antiandrogen therapy, which blocks the effect of the increased serum testosterone [Loblaw, 2004]. First generation antiandrogens such as flutamide, bicalutamide, and nilutamide bind to androgen receptors and competitively inhibit their interaction with testosterone and dihydrotestosterone. They are often used in an attempt to limit the clinical sequelae produced by the hormonal surge resulting from GnRH agonist treatment.

The most common adverse reactions (> 10%) reported for marketed formulations of leuprolide acetate depot in common use include the following examples:

- Leuprolide (leuprorelin) acetate 11.25 mg: weight fluctuation, hot flash, hyperhidrosis, muscle weakness, bone pain, decreased libido, erectile dysfunction, testicular atrophy, fatigue, injection site reaction [[Prostap 3 DCS, 2016](#)]
- Leuprolide acetate 22.5 mg: hot flashes, ecchymoses, erythema, fatigue, injection site burning, injection site paraesthesia [[Eligard, 2017](#)]

In post marketing experience, mood swings, depression, rare reports of suicidal ideation and attempt, rare reports of pituitary apoplexy have been reported. Leuprolide has been associated with mild liver enzyme elevations (generally transient and asymptomatic) during therapy in 3-5% of patients; values above 3 times the upper limit of normal are rare, being reported in less than 1% of recipients. A risk of developing or worsening diabetes has been reported in men receiving this class of drug.

The package insert (approved labeling) for the leuprolide acetate study drug provided for this study should be referenced for warnings, precautions, and safety information.

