
There are 2 separate evaluation criteria for the primary efficacy endpoint to support different regulatory requirements for assessing benefit:

- Evaluation Criterion 1: to determine whether the sustained castration rate for relugolix is greater than or equal to 90%. The lower bound of the 95% confidence interval for the cumulative probability of sustained testosterone suppression to castrate levels in the relugolix treatment group will be calculated and must be greater than or equal to 90% to meet this criterion.
- Evaluation Criterion 2: to establish the non-inferiority of relugolix compared to leuprolide acetate 3-M depot as assessed by the cumulative probability of sustained testosterone suppression to castrate levels. The lower bound of the 95% confidence interval for the difference in the cumulative probability of sustained testosterone suppression to castrate levels between the 2 treatment groups will be calculated and must be greater than or equal to the non-inferiority margin of -10% to meet this criterion.

The 2-sided type I error rate will be 0.05 for each individual evaluation criterion.

Secondary Efficacy Endpoints:

1. Castration rate: the cumulative probability of testosterone suppression to ≤ 50 ng/dL (1.7 nmol/L) prior to dosing on Week 1 Day 4, and prior to dosing on Week 3 Day 1;
2. Profound castration rate: the cumulative probability of testosterone suppression to ≤ 20 ng/dL (0.7 nmol/L) from Week 25 through Week 49;
3. PSA response rate: proportion of patients with a $\geq 50\%$ decrease in PSA from baseline at Week 3 and confirmed at Week 5;
4. Undetectable PSA rate: proportion of patients with PSA concentration < 0.2 ng/mL (0.2 μ g/L) at the Week 3 and Week 5 visits;
5. Time to testosterone recovery in approximately 100 relugolix-treated and approximately 50 leuprolide acetate-treated patients who complete 48 weeks of treatment and do not start alternative androgen deprivation therapy within 12 weeks after the last dose of relugolix or within 24 weeks following the last received injection of leuprolide acetate. Kaplan-Meier methods will be used to describe survival distributions;

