- Patients who have started alternative androgen deprivation therapy will not participate in the 60- and 90-day Follow-up visits. For approximately 100 patients receiving relugolix and approximately 50 patients receiving leuprolide acetate who complete 48 weeks of study drug treatment and, in the opinion of the investigator, can remain off androgen deprivation therapy for 90 days will be included in the testosterone recovery 60- and 90-day Follow-up visits.
- For patients assigned to the relugolix treatment arm, the patient should be called 7 days before their next visit to check on compliance with their study medication. Study drug accountability will be conducted at visits and results will be recorded as the primary source of study drug accountability.
- If patient terminates early from study treatment, the patient should be asked to come in as soon as possible and complete this visit.
- The informed consent form must be signed before any study-mandated procedures are performed.
- 12-lead ECGs should be read locally by a qualified physician.
- A complete physical examination should be performed. Visual acuity will be evaluated by a standard visual eye chart. The patient should wear any prescribed glasses or contacts during the visual acuity assessment. Patients whose presenting visual acuity score is 90 or lower at the screening visit should be encouraged to obtain a diagnostic evaluation from an eye care provider (ie, an ophthalmologist or an optometrist). Any findings (ie, diagnoses) from the eye examination should be recorded as medical history. Patients whose presenting visual acuity score at Week 25, Week 49, or Early Termination has decreased by 10 or more points from the screening visit should be referred to an ophthalmologist for a diagnostic evaluation. A copy of the ophthalmology consultation must be submitted to the sponsor.

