5.8. Blinding

Blinding is not applicable; this is a randomized open-label study.

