9.3.2. Secondary Endpoint Analyses

If the result of the primary endpoint is statistically significant, the secondary endpoints will be analyzed. The methods and procedures necessary to maintain a study-wide 2-sided type I error rate of 0.05 across primary and secondary endpoint testing will be described in the statistical analysis plan.

- Castration rate defined as the cumulative probability of testosterone suppression to ≤ 50 ng/dL (1.7 nmol/L) prior to dosing at Week 1 Day 4, and prior to dosing at Week 3 Day 1 will be summarized by treatment group using the Kaplan-Meier method;
- Profound castration rate defined as the cumulative probability of testosterone suppression of ≤ 20 ng/dL (0.7 nmol/L) while on treatment from Week 25 Day 1 through Week 49 Day 1 will be estimated for each treatment group using the Kaplan-Meier method. The difference in the cumulative probabilities between the relugolix group and the leuprolide acetate group will be provided, along with the 95% confidence interval calculated in the same manner as in the primary analysis of the primary endpoint;
- PSA response and percent change from baseline in PSA at Week 3 and Week 5 will be summarized and compared between the relugolix group and the leuprolide acetate group;
- Proportions of patients who have a PSA concentration < 0.2 ng/mL (0.2 μ g/L) at Week 25 will be summarized by treatment group. The proportions will be compared between the relugolix group and the leuprolide acetate group by constructing a 95% confidence interval for the difference in proportions;
- Time to testosterone recovery in approximately 100 patients randomized to relugolix and approximately 50 patients randomized to leuprolide acetate who complete 48 weeks of treatment and who do not start alternative androgen deprivation therapy within the following 12 weeks (or within 24 weeks following the last received leuprolide acetate 3-M depot injection) will be compared between the relugolix group and the leuprolide acetate group;
- Absolute values and changes from baseline in the scores of the EORTC-QLQ-C30 global health domain and the EORTC-QLQ-PR25 sexual activity and hormonal-treatment-related symptom subdomains will be summarized by treatment group. The least square means at Week 49 will be compared between the relugolix group and the leuprolide acetate group by constructing a 95% confidence interval for the difference in the least square means using a mixed model for repeated measures;

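### The testosterone recovery comparison is made in subsets chosen after randomisation by unblinded investigators, under conflicting cohort wordings, so it should be labelled non-randomised and adjusted for baseline factors

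*Protocol*

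**What the plan says.** Section 4.7 of the protocol, in both the 915-patient text and the amended 1100-patient text, states: "Testosterone recovery will be evaluated in approximately 100 patients randomized to relugolix and approximately 50 patients to leuprolide acetate". These are men "who complete 48 weeks of study drug treatment and, in the opinion of the investigator, are candidates for intermittent androgen deprivation therapy", who will not be offered alternative therapy on completing study treatment. Section 6.4 repeats the candidate rule for the 60- and 90-day visits. No section provides for random, consecutive or treatment-blind selection. Section 5.8 states: "Blinding is not applicable; this is a randomized open-label study".

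Section 9.3.2 says that recovery time "will be compared between the relugolix group and the leuprolide acetate group". It names no test, model or covariate for this endpoint and leaves further detail of the secondary analyses to the statistical analysis plan (SAP). The synopsis, under secondary efficacy endpoints, adds for this item: "Kaplan-Meier methods will be used to describe survival distributions".

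Section 2.2.4.3, on stopping GnRH agonist therapy, says that return of testosterone to baseline "may be related to the duration of GnRH agonist therapy, patient age, and other factors". Exclusion criterion 2 admits men with up to 18 months of earlier androgen deprivation. Section 9.1 makes region, metastatic disease and age (75 or younger versus older) the default factors for stratified efficacy analyses.

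**The concern.** Randomisation balances the 915 men, not a fraction of them picked out after treatment. Inclusion here rests on a judgement by someone who knows the assigned arm. Section 4.1 allows enzalutamide after confirmed PSA progression, which implies that the patient's PSA course is also known at the site. There is a plausible reason for the judgement to differ by arm. Section 2.2.4.2 tells investigators that in phase 2 about half of the relugolix patients had recovered testosterone 12 weeks after stopping, against 6% on degarelix. An investigator deciding who can safely be left untreated may weigh that.

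If the men taken off therapy differ between arms in age, baseline testosterone or earlier androgen deprivation, that difference would read as a drug effect on a secondary endpoint. A cohort definition that drops men who restart therapy during the recovery window adds a second route to bias, because restarting may itself follow from testosterone and PSA rising.

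**Working it through.** **Share of each arm.** Planned arms are 610 and 305, with 15% dropout (Section 9.9).
- Of those randomised: 100/610 = 50/305 = 16.4%.
- Of expected completers: 100/(610 × 0.85) = 100/518.5 = 19.3%, and 50/(305 × 0.85) = 50/259.25 = 19.3%.

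Roughly four in five completers are therefore outside the cohort. The protocol gives no power or effect size for the 100 and 50, so there is no stated figure to reproduce; the numbers simply follow the 2:1 allocation.

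**Who is in the cohort.** Four wordings stand in the amended text:
- Sections 4.7 and 6.4: investigator opinion that the man is a candidate for intermittent therapy.
- Section 1.1, footnote c: men who, "in the opinion of the investigator, can remain off androgen deprivation therapy for 90 days".
- Section 3 and the synopsis endpoint list: men with no plan to start alternative therapy, which is an intention.
- Section 9.3.2 and the synopsis efficacy item: men "who do not start alternative androgen deprivation therapy within the following 12 weeks", which is an event after cohort entry.

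The first three can be settled at end of treatment. The last cannot be known until the recovery window has closed.

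**What the default strata cover.** Region (3) × metastatic disease (2) × age (2) = 12 cells. Age enters only at a 75-year cut. Baseline testosterone and earlier androgen deprivation do not enter.

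**Illustration on the hazard scale, no drug effect.** All inputs here are assumptions. A factor halves the recovery hazard and is present in shares pA and pB of the two selected groups. Approximate unadjusted hazard ratio = (1 − 0.5pA)/(1 − 0.5pB).
- 20% versus 40%: 0.90/0.80 = 1.125.
- 15% versus 45%: 0.925/0.775 = 1.194.

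With E recoveries at 2:1, z = ln(HR) × √(E × 2/9), and the two-sided rejection rate is 1 − Φ(1.96 − z) + Φ(−1.96 − z). For E from 60 to 90:
- HR 1.125: z = 0.43 to 0.53, rejection 7.1% to 8.2%.
- HR 1.194: z = 0.65 to 0.79, rejection 9.9% to 12.4%.

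A log-rank simulation (100 versus 50 men, visits at days 30, 60 and 90, 50% recovery by day 90 in men without the factor) gave 7.1% and 9.9%, against 5.5% with no imbalance.

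**Illustration on the proportion scale, no drug effect.** Bias = (recovery in favourable men − recovery in unfavourable men) × imbalance in shares. Shares are centred on 50%, with a pooled two-sided z-test on 100 versus 50. The ranges are for imbalances of 10 to 30 points.

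| Recovery, favourable vs unfavourable | Bias (points) | Rejection rate |
|---|---|---|
| 60% vs 40% | 2 to 6 | 5.6% to 10.6% |
| 60% vs 30% | 3 to 9 | 6.3% to 17.8% |
| 70% vs 20% | 5 to 15 | 8.8% to 40.9% |

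The spread shows that the answer is set by the assumptions.

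**The case against.** The best defence is that covariates for one secondary endpoint belong in the SAP, which was not available here. A reader might infer from the protocol's silence that no adjustment is planned. The documents do not support that: Section 9.3.2 defers detail, and the default in Section 9.1 would bring in age at 75 years if the comparison is stratified. Nor does Section 9.3.2 say that Kaplan-Meier methods will be used to test the arms against each other; that method is named in the synopsis, for description.

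Three further inferences go beyond the text. Investigator opinion is required, but nothing says that men are picked at Week 49 or in a partisan way. The sentence on factors behind recovery speaks of duration of GnRH agonist therapy, with no mention of pre-study therapy or baseline testosterone, and says only that a relation may exist. The advantages that Section 2.1 lists for relugolix are onset, absence of flare and oral dosing; faster recovery is not among them.

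It is also fair that the same selection wording applies to both arms, and that every imbalance used above is assumed.

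What remains is fixed by the protocol itself: membership by unblinded opinion after randomisation, a planned between-arm comparison with no label to mark its status, and conflicting membership rules. The SAP can choose a model, but it cannot make the subsets randomised.

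**Conclusion.** The point holds for what the protocol fixes. The recovery contrast compares two post-randomisation subsets, each about 16% of its planned arm, selected by unblinded judgement. The cohort is defined in ways that disagree, and one of them conditions on an event during follow-up. Confounding is possible, and its size and direction cannot be known in advance.

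The spurious hazard ratios of about 1.13 to 1.19, with rejection rates of about 7% to 12%, illustrate what imbalances of 20 to 30 points in a factor that halves the recovery hazard would do with 60 to 90 recoveries. A reader might take them as the trial's actual type I error; they are not. The primary endpoint is unaffected. This is a change that should be made to a secondary analysis.

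**What to change.** In Section 9.3.2, and wherever the cohort is defined:

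1. Describe the result as a comparison of non-randomised subsets.
2. Make the main comparison a Cox model, or covariate-standardised Kaplan-Meier curves, adjusted for a short list of baseline factors: age, baseline testosterone, and prior androgen deprivation as recorded in the prostate cancer history. Do not also split about 150 men across all 12 strata. Give the unadjusted curves as supportive.
3. Tabulate these factors by arm for the recovery cohort.
4. Reconcile the four cohort wordings so that analysis membership is set at end of treatment and does not depend on later starts of therapy.

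The cost is wording, with no added patients or visits. Age and testosterone are already scheduled. Duration of prior androgen deprivation has to be known for exclusion criterion 2, but the protocol does not say that months are captured as data: Section 6.6.2.6 records medications only from 30 days before first dose, and the detailed cancer history is not itemised. The form should be checked.

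The limit should be stated with the result: baseline adjustment removes measured confounding only and cannot correct selection on the on-treatment PSA course.
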